2203 Racial and ethnic minorities will be recruited into the study. We anticipate that the representation of

2204 racial and ethnic minorities will correspond to the fraction of minorities in the population presenting to
2205 the participating clinics as patients. Recruitment will be monitored to ensure that the representation of
2206 minority groups parallels the racial/ethnic composition of patients seen for visits at LURN Clinical Sites.

2207 **6.5 Inclusion of Children**

2208 Children under the age of 18 will not be enrolled into this study as the LURN physicians do not have
2209 children in the practices.

2210 **6.6 Data Safety and Monitoring Plan**

2211 Accepted principles of data and safety monitoring will be observed throughout the conduct of the LURN
2212 study. The NIH has appointed an independent External Expert Panel (EEP) that will provide study
2213 oversight. The EEP will review the study protocol prior to enrollment and will also review all subsequent
2214 protocol revisions. The EEP will also evaluate the occurrence of adverse events related to study
2215 participation as well as study accrual updates that include the demographics, clinical characteristics, and
2216 symptom profiles of enrolled patients to ensure maintenance of recruitment targets and clinical
2217 relevance of the study population.

2218 LURN principal investigators will be responsible for monitoring the enrollment of subjects, submission of
2219 data to the DCC, and monitoring and reporting of adverse events related to study participation. The DCC
2220 will be responsible for monitoring for effective conduct of the protocol and accurate and timely data
2221 submission.

2222 IRBs will be provided feedback on a regular basis.

2223 Training of study coordinators and study monitoring activities will be conducted by the DCC to ensure
2224 patient confidentiality and privacy and to maximize the reliability, accuracy, and timeliness of study
2225 data.

2226 The LURN Clinical Sites, the DCC, and relevant research center staff will conduct regular meetings to
2227 review recruitment/enrollment progress, data collection activities, and participant retention. The DCC
2228 will produce regular reports regarding enrollment, data quality, and timeliness and share the reports
2229 with NIDDK, the Steering Committee, and the participating clinical center. Data will be routinely

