531 **Table 3: Estimated number of patients available for recruitment from LURN clinical sites**

	Men	Women	Total
Monthly Totals	260	183	443
Yearly Totals	3120	2196	5316

532 We plan to recruit at least 500 men and 500 women and over a 12-month period. We will review
533 quarterly study accrual to confirm our anticipated timeline, update our estimate of eligible patients
534 across the LURN, review recruitment of planned subgroups of patients (i.e., obese patients and
535 diabetics), and update overall recruitment expectations. If our interim assessment indicates that fewer
536 than 10% of participants are obese or have diabetes, we will target additional recruitment to increase
537 representation of these subgroups in the cohort. Additional recruitment may result in a total sample of
538 up to 600 men and up to 600 women, and may extend the recruitment period by 6 months for a total of
539 18 months. After we have reached our target accrual for the observational cohort, described above,
540 additional participants will continue to be recruited for Project 1B (Neuroimaging and Sensory Testing
541 substudy). These additional participants will undergo only the baseline visit described in Table 2 and
542 none of the follow-up visits.

543 Rather than presenting power calculations for each hypothesis, we present four series of power
544 calculations for the four basic hypothesis tests we anticipate using: t-tests, logistic regressions,
545 correlations, and chi-square tests (see examples below). All calculations are based on a significance level
546 of 0.05. The power calculations presented below assume that associations are unadjusted for
547 confounding factors. Adjusting analyses using multivariable regression or other techniques will provide
548 at least as much power as an unadjusted analysis and in many cases substantially more power.

549 In Tables 4 through 7, power is presented for the entire sample size (n = 1000); for group comparisons,
 550 subgroup sample sizes are reported in the left-most column. In addition to analyses using the entire
 551 sample, certain analyses may be performed separately for men and women. Power calculations for
 552 analyses stratified by sex (using only 500 men or 500 women) are presented in parentheses.

553 Table 4 provides power calculations for two-sample t-tests that will be used to test hypotheses
 554 comparing continuous outcomes (e.g., symptom severity, health-related quality of life) between two

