 598 will include frequencies and percentages for categorical variables, and means, standard deviations, and
 599 ranges for continuous variables. Variables will also be examined separately by subgroups, such as by
 600 LURN clinical site sex, race and ethnicity.

601 We will examine the distribution of responses on health-related quality of life questionnaires and
 602 instruments that assess pelvic floor function, and psychological and sleep disorders. If the outcome
 603 variables are normally distributed, we will use t-tests to compare the mean values of the parameters
 604 among men and women and Pearson correlations to examine associations with symptom severity. If the
 605 outcome variables are not normally distributed, we will use Wilcoxon rank sum tests or other non-

606 parametric tests to compare men and women, and Spearman rank correlations to examine associations
607 with symptom severity. If outcomes are binary or categorical, we will use chi-square tests, logistic
608 regression, or multinomial regression to examine associations.

609 Using the same techniques, we will also examine whether patients differ in their LUTD symptom severity
610 and bother and self-report of pelvic floor function and psychological factors when stratified by age, sex,
611 race/ethnicity, presence of diabetes mellitus, and presence of obesity, and whether clinicians'
612 impression/diagnosis exhibits variability in urinary symptoms, patient demographic and clinical
613 characteristics, pelvic floor function, and psychological factors.

614 Additional investigations of subgroup differences will use multivariable analyses to control for
615 demographic characteristics and multiple measures of surgical history, obstetric history, comorbidities,
616 and bother with symptoms at the same time. If the outcome measure is binary or categorical, logistic or
617 multinomial logistic regression will be used. If the outcome measure is continuous, we will use linear
618 regressions. Multivariable models will be created using a best subsets approach, with the final model
619 being the one with the highest likelihood score statistic or explained variance, provided that all
620 covariates are statistically significant at $p < 0.05$. Multivariable models will be adjusted for LURN clinical
621 sites whenever appropriate.

622 **Aim 2**

623 The goal of Aim 2 is to identify subgroups or clusters of study participants. Anticipated subgroups for

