1478 T-tests will be used to compare functional connectivity, diffusivity and anisotropy, sensitivity
1479 thresholds and tolerances between urgency patients and controls. **Table 13** shows the statistical power
1480 for various effect sizes. The power calculations presented below assume that associations are
1481 unadjusted for confounding factors. Adjusting analyses for age, sex, or other characteristics of the
1482 samples will provide at least as much power as an unadjusted analysis and in many cases substantially
1483 more power.

1484
1485

1486

1487

1488 **Table 13: Statistical power to detect the given effect size using two-sample t-tests using the entire sample,**
 1489 **n=252 participants total.**

Number enrolled	Effect size		
	0.4	0.5	0.6
168 with urgency, 84 controls	0.847	0.961	0.994

1490 Note: An effect size of 0.4 would be achieved assuming a whole-sample average correlation standard deviation of
 1491 0.2, a control group mean of 0.5, and a group mean of 0.58. For an effect size of 0.6, the group mean would be
 1492 0.62.

1493 Since RSfMRI and DTI have never been published in any urinary urgency studies, it is difficult to calculate
 1494 the sample size precisely. Based on other RSfMRI and DTI studies, we estimate that n=84 for each of the
 1495 three groups (urgency with urgency incontinence, urgency without urgency incontinence, and matched
 1496 healthy controls) will allow us to detect an effect size of 0.5 with >90% statistical power, using two-tailed
 1497 analysis with alpha=0.05.

1498 Statistical power to assess associations of incontinence severity and functional connectivity, diffusivity
 1499 and anisotropy, sensitivity thresholds and tolerances will be based on correlation coefficients as a
 1500 proxy for the linear regression used at the analysis stage.

1501 **Table 14: Statistical power to detect the given correlation among urgency patients, n=168 participants total**

Number enrolled	Correlation coefficient (r)		
	0.20	0.25	0.30
84 with urgency incontinence versus 84 without urgency incontinence	0.743	0.908	0.979

1502 We estimate that n=84 for each of the sub-groups (with urgency incontinence, versus without urgency
 1503 incontinence) will allow us to detect a correlation coefficient of 0.25 with >90% statistical power,
 1504 assuming alpha=0.05 (see **Table 14**).

1505 **4.3.7 Statistical Analysis**

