1506 First, we will report descriptive statistics of the characteristics of the participants. Descriptive statistics
 1507 will include frequencies and percentages for categorical variables, and means, standard deviations, and
 1508 ranges for continuous variables. Variables will also be examined separately by subgroups, such as by
 1509 LURN clinical site sex, race and ethnicity.

1510 **Aim 1**

1511 Aim 1 focuses on examination of RSfMRI and DTI results. We will examine the distribution of
 1512 incontinence severity, diffusivity and anisotropy. Functional connectivity will already be normalized as
 1513 described in section 4.3.4. For ROI pairs of interest, we will use t-tests to compare the mean values of
 1514 the subject-specific correlation estimates among urgency patients and controls. We will use linear
 1515 regression to examine associations of these connectivity measures with incontinence severity, adjusted
 1516 for the subject's age as needed. Additional investigations will use linear regression to control for other

1517 demographic characteristics and potentially confounding variables. Variable inclusion will be guided by a
1518 best subsets approach, with the final model being the one with the highest likelihood score statistic or
1519 explained variance in which all covariates are statistically significant at $p < 0.05$. Multivariable models
1520 will be adjusted for LURN clinical sites whenever appropriate. We will also consider the distribution of
1521 activation levels at each ROI and compare the distribution among subject groups both visually and using
1522 t-tests to test whether mean levels differ between subjects with vs. without a full bladder, between
1523 those with vs. without urinary urgency, and between those with urgency with vs. without incontinence.

1524 Between-groups comparison will also be performed in males and females separately: urgency as a whole
1525 [n=84 each sex] versus control [n=42 each sex].

1526 **Aim 2**

1527 In Aim 2, we will be focused on sensory testing results. We will examine the distribution of sensitivity
1528 thresholds and tolerances. If the thresholds and tolerances are normally distributed or can be
1529 transformed to achieve normality, we will use t-tests to compare the mean values among urgency
1530 patients and controls and Pearson correlations to examine associations with incontinence severity. If the

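### Sections 3.4.9 and 4.3.6 wrongly promise that adjustment never costs power, and the best-subsets rule in 3.4.10 and 4.3.7 is unsuited to confounder control

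*Protocol*

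**What the plan says.** **Power.** Section 3.4.9 sets the cohort size ("We plan to recruit at least 500 men and 500 women") and works at the 0.05 level throughout ("All calculations are based on a significance level" of 0.05). It states the basis of its tables openly: "The power calculations presented below assume that associations are unadjusted for" confounding factors. It then says that multivariable regression or other adjustment will give "at least as much power as an unadjusted analysis and in many cases substantially more power". Section 4.3.6 repeats this for Project 1B, naming age, sex and other features of the participants: adjusting for these in the "samples will provide at least as much power as an unadjusted analysis and in many cases substantially" more. Project 1B uses a two-tailed "analysis with alpha=0.05".

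**Model building.** Section 3.4.10 (Aim 1) uses multivariable models to control for demographics, surgical and obstetric history, comorbidities and symptom bother. The final model is chosen by best subsets, "being the one with the highest likelihood score statistic or explained variance, provided that all" covariates reach p<0.05. Section 4.3.7 (Aim 1) applies the same rule to potential confounders: a "best subsets approach, with the final model being the one with the highest likelihood score statistic or" explained variance, again with all covariates at p<0.05.

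**What is protected from selection.** Clinical site is adjusted for where judged appropriate. In Project 1B age is adjusted for where needed. Under 3.4.10.1, variables that predict missingness of an outcome enter the analyses of that outcome. The protocol does not say whether the exposure under test is forced into the model.

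**The concern.** The no-loss statement suits covariates that predict the outcome and are unrelated to the exposure, as in a randomised trial. Here the exposures (diabetes, obesity, age group, urgency) are observed, and the adjustment is for confounders, which are related to exposure by definition. The protocol expects such relations itself: Hypothesis 1d(e) predicts more comorbid conditions in diabetic patients, and 3.4.10 lists comorbidities among the adjustment variables. A reader who trusts the sentence will take the tabulated power as a floor for the adjusted results.

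The selection rule raises a second problem. Whether a covariate reaches p<0.05 does not tell whether omitting it biases the exposure effect. A confounder with a small effect on the outcome but a clear correlation with the exposure can fail the test and still leave bias behind. The p-values printed for the chosen model also take no account of the search.

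**Working it through.** **1. Reproducing the protocol's figures.** Two-sided two-sample t-test at 0.05, with noncentrality d × sqrt(n1·n2/(n1+n2)):

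- 500 vs 500, d = 0.2: 0.2 × sqrt(250) = 3.162; power 0.885 (Table 4: 0.885).
- 100 vs 900, d = 0.3: 0.3 × sqrt(90) = 2.846; power 0.811 (Table 4: 0.811).
- 168 vs 84, d = 0.4: 0.4 × sqrt(56) = 2.993; power 0.847 (Table 13: 0.847).

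All cells of Tables 4 and 13 reproduce, as does Table 7; Table 6 agrees within 0.001. Table 5 rests on a logistic method that the protocol does not name. A simple approximation did not match it, and it is not used here.

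**2. Effect of adjustment.** In a linear model the variance of the exposure effect is multiplied by (1 − R2y)/(1 − R2x). R2x is the share of exposure variance explained by the covariates, and R2y the share of residual outcome variance they explain. At the same effect size, the noncentrality is multiplied by sqrt((1 − R2x)/(1 − R2y)). Both shares are assumptions.

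Example: 500 vs 500, R2x = 0.3, R2y = 0 gives 3.162 × sqrt(0.7) = 2.646. Less the critical value of about 1.962 this leaves 0.684, so power is 0.753.

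| R2x | R2y | 500 vs 500, d 0.2 | 100 vs 900, d 0.3 | 168 vs 84, d 0.4 |
|---|---|---|---|---|
| 0 | 0 | 0.885 | 0.811 | 0.847 |
| 0.1 | 0 | 0.850 | 0.770 | 0.808 |
| 0.2 | 0 | 0.807 | 0.720 | 0.760 |
| 0.3 | 0 | 0.753 | 0.662 | 0.704 |
| 0.2 | 0.05 | 0.826 | 0.742 | 0.781 |
| 0.1 | 0.1 | 0.885 | 0.811 | 0.847 |
| 0 | 0.2 | 0.942 | 0.889 | 0.915 |

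Power therefore falls if R2x exceeds R2y, is unchanged if they are equal, and rises if R2y is larger.

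**3. The selection rule.** Simulated by all-subsets linear regression: the final model has the highest R2 among subsets with every covariate at p<0.05. The true exposure effect is zero; n = 1000 or 252; 1000 to 4000 runs per setting (Monte Carlo error 0.3 to 1.5 percentage points). Candidates were one confounder plus three noise variables, or four confounders plus two. Confounder strength and correlation with the exposure are assumed. Because the protocol is silent on the exposure's place, three readings were run: (A) the exposure is one of the candidates; (B) it is forced in and only the covariates must reach p<0.05; (C) covariates are selected first and the exposure is added afterwards. Entries are false-positive rates.

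| n | Confounders | Correlation | Effect (SD) | Fixed full model | A | B | C |
|---|---|---|---|---|---|---|---|
| 1000 | 1 | 0 | 0.10 | 0.043 | 0.042 | 0.042 | 0.042 |
| 1000 | 1 | 0.5 | 0.20 | 0.053 | 0.054 | 0.054 | 0.054 |
| 1000 | 1 | 0.5 | 0.05 | 0.051 | 0.082 | 0.104 | 0.057 |
| 1000 | 4 | 0.3 | 0.05 | 0.045 | 0.111 | 0.183 | 0.088 |
| 1000 | 4 | 0.5 | 0.05 | 0.061 | 0.176 | 0.391 | 0.110 |
| 1000 | 4 | 0.5 | 0.10 | 0.050 | 0.078 | 0.185 | 0.059 |
| 252 | 4 | 0.3 | 0.10 | 0.045 | 0.117 | 0.178 | 0.087 |
| 252 | 4 | 0.5 | 0.10 | 0.048 | 0.173 | 0.383 | 0.105 |

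Over all four-confounder settings the rate was 7% to 18% under A, 9% to 39% under B and 6% to 11% under C. A separate run with five weak confounders and the exposure as a candidate gave 7% to 21%. With five confounders correlated only 0.1 to 0.2 with the exposure, n = 1000, it was 4% to 8%.

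Loss of a single real confounder (correlation 0.3 to 0.7, readings A and B): at n = 1000, omitted in 65-80% of runs at effect 0.05, 11-39% at 0.10 and 0-7% at 0.15-0.20. At n = 252 and effect 0.10, omitted in 66-79%.

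**The case against.** **The tables are labelled unadjusted, and the adjusted models are supplementary.** Both true. A reader might infer that the tables overstate power; they do not, because they claim only unadjusted power. What fails is the sentence that carries them over to adjusted analyses. Supplementary or not, the adjusted models are the ones that address confounding.

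**Project 1B is protected by design.** Sex numbers are equal in every group and the groups are age-matched within sex, so R2x is near zero for those two covariates and the sentence is roughly right for them. Any loss in the last column of the power table must come from the other characteristics that 4.3.6 mentions.

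**The inflation depends on invented scenarios.** This stands. A reader might say that the rule triples the false-positive rate; the documents do not supply the inputs for any single multiple. Strong confounders are kept at n = 1000, and weakly correlated ones do little harm. In the four-confounder settings the rule also does far better than no adjustment: at n = 1000, correlation 0.5 and effect 0.05 the unadjusted test rejects in 89% of runs. The two halves also use different assumptions. Five confounders correlated 0.3 to 0.5 with the exposure, if independent given it, imply R2x of about 0.33 to 0.63, at or above the top of the power range shown.

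**Logistic models.** A reader might add that adjustment there never reduces the standard error, so power must fall. That does not follow: with covariates unrelated to exposure, the conditional effect moves away from the null. The power figures here are for linear models only.

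**Confounder lists belong in the SAP.** The lists may. The p<0.05 retention rule, however, is fixed in the protocol, so an unseen SAP does not excuse it. The provisions for site, age and predictors of missingness help but do not protect the remaining confounders.

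**Conclusion.** The point holds in two limited parts. First, the unconditional power statement in 3.4.9 and 4.3.6 is wrong for confounder adjustment. With R2y = 0 and R2x between 0.1 and 0.3, the three examples lose about 4 to 15 percentage points; the protocol's 10-90 example (diabetes) at effect size 0.3 goes from 0.811 to 0.770, 0.720 or 0.662. These losses assume an unchanged effect size and disappear once R2y reaches R2x.

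Second, the best-subsets rule can drop weak real confounders and gives p-values that ignore the search. With the exposure as a candidate, the false-positive rate runs from about 5% (no, strong or weakly correlated confounding) to roughly 10-20% (several weak confounders correlated 0.3 to 0.5 with the exposure), against about 5% for a fixed model. It can be higher if only the exposure is forced in. The scenarios are assumptions, so the result is a range and not a property of this cohort.

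**What to change.** In 3.4.9 and 4.3.6, delete the sentence, or limit it to covariates that explain more of the outcome than of the exposure. Say that adjusted power may be lower, and show a range over R2x and R2y.

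In 3.4.10 and 4.3.7, for models that test a hypothesis, keep the exposure and a confounder set pre-specified per hypothesis, whatever their p-values. Forcing in the exposure alone is not enough, as reading B shows. Leave out of the set any variable that the hypothesis treats as an outcome of the exposure, for example comorbidity when the exposure is diabetes (Hypothesis 1d(e)). Restrict best subsets to models labelled exploratory or predictive.

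The cost is protocol wording, a slightly less favourable statement of adjusted power and a few more terms per model. No extra participants or visits are needed.

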285 associated with patient responses on the LUTS Tool.

286 **Aim 2:** Based on cross-sectional data, identify distinct subgroups (clusters) of study participants based
287 on their urinary symptoms assessed by the LUTS Tool, CASUS, clinical assessments, pelvic floor function
288 and psychological factors utilizing cluster analysis and classification and regression trees (CART).

289 **Hypothesis 2a:** Distinct clusters of study participants can be identified that will differ in urinary
290 symptoms, results from clinical assessments, patient-reported pelvic floor function, and
291 psychological factors.

292 **Hypothesis 2b:** Urinary symptoms within these LURN clusters will have higher prevalence of
293 mixed and more severe urinary symptoms compared with clusters identified in population-
294 based studies.

295 **Hypothesis 2c:** Clusters of study participants derived from the LURN observational cohort will
296 exhibit unique results on targeted phenotyping.

297
298 **Exploratory Question 2a:** Will the number and types of symptom clusters identified from CASUS
299 be similar to the number and types identified by the LUTS Tool?

300 **Aim 3:** To prospectively assess the treatments recommended by LURN physicians and associated
301 changes in urinary symptoms and urinary quality of life in men and women seeking care for LUTS.

302 **Hypothesis 3a:** Symptom changes, as determined by the LUTS Tool and CASUS, and stratified by
303 the selected treatments, will be associated with specific subgroups of study participants,
304 including those defined at study entry by age, sex, presence of diabetes, and presence of
305 obesity.

306 **Hypothesis 3b:** Symptom changes, as determined by the LUTS Tool stratified by the selected
307 treatments, will be associated with pelvic floor function and psychological factors determined at
308 study entry.

309 **Hypothesis 3c:** Patient clusters developed in Aim 2 will be associated with initial treatment
310 selection by LURN physicians and response to LUTD-specific treatments as measured by the
311 LUTS Tool.

312 **Hypothesis 3d:** Patients that respond to LUTD-specific treatment will move from one LURN
 313 symptom cluster to another as a result of lessening of symptom severity.

314 **Aim 4:** To evaluate the completion, response variability, and potential overlap of the CASUS items.

315 **Exploratory Question 4a:** How do rates of missing items for the CASUS compare with rates for

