 555 groups of patients (e.g., men and women) for several potential sample sizes. Differences between
 556 groups are expressed in terms of effect sizes. An effect size of 0.25 can be considered small and an
 557 effect size of 0.5 can be considered moderate.

558 **Table 4: Statistical power to detect the given effect size using two-sample t-tests using the entire sample (and**
 559 **stratified by sex, in parentheses)**

Total N enrolled	Effect size			
	0.2	0.3	0.4	0.5
Subgroups are 50%-50%*				
500 per group	0.885	0.997	>0.999	>0.999
(250 women per group)	(0.607)	(0.917)	(0.994)	(>0.999)
Subgroups are 30%-70%**				
1000: 300 and 700	0.825	0.991	>0.999	>0.999
(150 and 350 women)	(0.534)	(0.866)	(0.983)	(>0.999)
Subgroups are 10%-90%***				
1000: 100 and 900	0.474	0.811	0.966	0.997
(50 and 450 women)	(0.268)	(0.519)	(0.764)	(0.917)

560 *An example of a 50-50 split is dividing the sample at the median age and comparing older patients to
 561 younger patients.

562 ** An example of a 30-70 split is patients with BMI \geq 30 compared with patients with BMI < 30.

563 *** An example of a 10-90 split is patients with diabetes compared with patients without diabetes.

564 Table 5 provides power calculations for logistic regressions that will be used to test hypotheses
 565 comparing continuous predictors (e.g., psychological stress) and dichotomous outcomes (e.g., LUTD with
 566 and without urinary incontinence) for several potential sample sizes. Differences between groups are
 567 expressed in terms of the odds ratio for a 1 standard deviation increase in the predictor.

568 **Table 5: Statistical power to detect the given odds ratio using logistic regression using the entire sample (and**
 569 **stratified by sex, in parentheses)**

	Odds ratio			
Total N enrolled	1.2	1.3	1.4	1.5
Outcome is 50%-50%				
500 per group	0.768	0.971	0.998	>0.999
(250 women per group)	(0.478)	(0.779)	(0.936)	(0.986)
Outcome is 30%-70%				
1000: 300 and 700	0.696	0.994	0.995	>0.999
(150 and 350 women)	(0.416)	(0.709)	(0.894)	(0.971)
Outcome is 10%-90%				
1000: 100 and 900	0.370	0.653	0.858	0.957
(50 and 450 women)	(0.210)	(0.384)	(0.573)	(0.738)

570
 571 Table 6 provides power calculations for correlations that will be used to test hypotheses comparing two
 572 continuous variables (e.g., psychological stress and severity of symptoms; Aims 4 and 5) for several
 573 potential sample sizes.

574

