674 After growing each CART, we will prune the tree to avoid over-specification. This will be done by cross-
675 validating the tree on a sample of the data and will be used to minimize expected misprediction error.

676 **Aim 3**

677 Aim 3 involves longitudinal hypotheses about LUTS, health-related quality of life, pelvic floor function,
678 and psychological factors. Associations between patient clusters and treatment selection will be
679 examined as described in as part of Aim 2. We will examine changes in symptoms over time (Hypotheses
680 3a and 3b) using repeated measures ANOVA or mixed models with random within-person effects.
681 Repeated measures ANOVA and mixed models with random within-person effects will allow for analysis
682 of a cohort of patients with multiple follow-up visits within the 12-month study time frame of the LURN
683 prospective observational cohort. To address Hypothesis 3c, we will categorize patients into types of
684 treatment: medication, surgical intervention, watchful waiting, and other. We will examine the
685 associations between symptom cluster and these categories of treatments using chi-square tests and
686 multinomial regressions. Patients will also be categorized into a treatment-responsive group and a
687 treatment-unresponsive group. We will examine associations between treatment response and cluster,
688 as well as other patient characteristics, using logistic regression. To address Hypothesis 3d, we will use
689 multinomial logistic regressions to predict symptom cluster at 12 months using baseline cluster and
690 treatment responsiveness, controlling for patient characteristics.

691 **Aim 4**

692 For the baseline and 12 month assessments of the CASUS, we will compute rates of missingness
693 separately for each item and compare these to similarly computed rates of missingness for items from

694 the other self-report instruments (Exploratory Question 4a). We will examine distributions of item
695 responses to identify any items that have little or no variability (Exploratory Question 4b). Finally, we
696 will compute the Pearson (or Spearman) correlations between all pairs of CASUS items separately at
697 baseline and the 12 month assessments, along with their 95% confidence intervals (Exploratory
698 Question 4c). Any pair of items with a correlation $\geq .90$ will be flagged for discussion by the LURN

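### For Hypothesis 3c, cluster differences in treatment response are tested only on a responsive/unresponsive split of a graded outcome, which costs power when effects are small or groups are small

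*Protocol*

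**What the plan says.** Hypothesis 3c (Protocol 3.3, Aim 3) has two parts. It links the clusters to initial treatment "selection by LURN physicians and response to LUTD-specific treatments as measured by the" LUTS Tool. Section 3.4.7 describes that instrument as grading the severity and bother of 18 symptoms.

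For the response part, section 3.4.10 (Aim 3) states: "Patients will also be categorized into a treatment-responsive group and a" "treatment-unresponsive group. We will examine associations between treatment response and cluster", together with other patient characteristics, by logistic regression. It gives no cut-off and no reason for the split.

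The same paragraph analyses symptom change under Hypotheses 3a and 3b by repeated measures ANOVA or mixed models. Under Aim 4, mean change in LUTS Tool items is examined by treatment status, not by cluster. Hypothesis 3d uses treatment responsiveness as a predictor of the 12-month cluster.

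On power, section 3.4.9 says: "Rather than presenting power calculations for each hypothesis, we present four series of power" calculations by type of test. Table 4 (t-tests) covers effect sizes of 0.2, 0.3, 0.4 and 0.5, and Table 5 covers logistic regression. Neither is tied to Aim 3.

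**The concern.** Splitting a graded outcome into two groups discards the degree of improvement. A patient who just passes the cut counts the same as one whose symptoms resolve.

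The primary objective in section 3.3 is to find subgroups that are clinically relevant. Whether clusters respond differently to treatment is one of the most direct tests of that relevance. As written, this question gets the less sensitive analysis, while age, sex, diabetes, obesity, pelvic floor and psychological factors (3a and 3b) get the graded one.

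This is not detail left to an SAP. The protocol itself fixes both the binary outcome and the model. An SAP could supply the cut-off, but it could not recover the lost information without adding a different analysis.

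**Working it through.** **Inputs from the protocol.**
- Sample size, section 3.4.9: "We plan to recruit at least 500 men and 500 women and over a 12-month period", so N = 1000.
- Significance level 0.05, section 3.4.9. Sidedness is not stated for Project 1A; two-sided reproduces Table 4.
- Effect sizes d from Table 4. I add 0.25, which section 3.4.9 calls small.

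**Assumptions, because the protocol does not fix them.** One roughly normal LUTS Tool change score, two clusters, all patients followed, and an overall responder rate of 50%, 40% or 30%.

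**Step 1: reproduce Table 4.** For a two-sided two-sample t-test the noncentrality is d × √(n₁n₂/(n₁+n₂)). For 500 v 500 at d = 0.2 this is 0.2 × √250 = 3.162 on 998 degrees of freedom, giving power 0.885. Table 4 prints "500 per group 0.885 0.997 >0.999 >0.999" for this row. All 24 cells of Table 4 reproduce.

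**Step 2: split the same outcome.** Choose the cut c so that the overall responder rate is r. Then p₁ = 1 − Φ(c − d) and p₂ = 1 − Φ(c). The power of the two-proportion test is Φ[(p₁ − p₂ − 1.96·s₀)/s₁], where s₀ is the pooled and s₁ the unpooled standard error.

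For 500 v 500 at d = 0.2:
- r = 50%: c = 0.100, p₁ = 0.540, p₂ = 0.460, s₀ = 0.0316, s₁ = 0.0315. Power = Φ[(0.0797 − 0.0620)/0.0315] = 0.713, a loss of 17.2 points.
- r = 40%: 0.439 v 0.361, power 0.702, a loss of 18.3 points.
- r = 30%: 0.335 v 0.265, power 0.668, a loss of 21.7 points.

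A Wald test of the log odds ratio, which mirrors the planned logistic regression, agrees within 0.003 in these cases.

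**Step 3: other effect sizes and group sizes, 30-50% responders.**

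| Groups | d | Graded | Split | Loss (points) |
|---|---|---|---|---|
| 500 v 500 | 0.2 | 0.885 | 0.668-0.713 | 17.2-21.7 |
| 500 v 500 | 0.25 | 0.977 | 0.849-0.883 | 9.3-12.8 |
| 500 v 500 | 0.3 | 0.997 | 0.948-0.966 | 3.1-4.9 |
| 500 v 500 | 0.4 | >0.999 | 0.998-0.999 | 0.1-0.2 |
| 500 v 500 | 0.5 | >0.999 | >0.999 | about 0 |
| 300 v 700 | 0.2 | 0.825 | 0.607-0.636 | 18.9-21.8 |
| 250 v 250 | 0.3 | 0.917 | 0.717-0.762 | 15.6-20.0 |
| 100 v 900 | 0.3 | 0.811 | 0.615-0.627 | 18.5-19.7 |

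**Sensitivity.** At a 20% responder rate the loss for 500 v 500 at d = 0.2 rises to 28.8 points (power 0.597). With three to five equal clusters, N = 1000 and Cohen's f = 0.1 (the equivalent of d = 0.2 for two equal groups), it is 20.5-22.0 points at 50% responders and 25.1-26.4 at 30%. Two clusters is therefore not a worst case.

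**Step 4: which graded term to test.** The gain above belongs to the cluster effect. A cluster by treatment type interaction is a different and weaker test. With two clusters of 500 and a share q of each on one treatment, the standard error of the interaction contrast in SD units is √[2(1/(500q) + 1/(500(1−q)))].
- q = 0.5: SE 0.126. A contrast of 0.2 SD gives z = 1.58 and power about 0.35.
- q = 0.1, the share section 3.4.6 anticipates for planned surgery: SE 0.211, z = 0.95 and power about 0.16.

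**The case against.** A fair defence has five parts.

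- **No design effect is missed.** A reader might infer that 0.2 is the effect the study was designed around and that 17-22 points is the general cost. The protocol does not support that. Table 4 is a generic grid, no power is claimed for 3c, and 0.2 lies below what section 3.4.9 calls small. In the full cohort the split still has 0.85-0.88 power at 0.25. This objection stands and limits the size of the point. It does not remove the loss in smaller or unequal groups, and section 3.4.9 foresees sex-specific analyses while section 3.4.10 leaves the number of clusters open.
- **Graded change is kept elsewhere.** A reader might infer that patient characteristics are tested only against the binary outcome. That is not so: 3a and 3b model symptom change for most of them. What remains is the cluster comparison in 3c.
- **The score may not be continuous.** The protocol defines no LUTS Tool total or change score, and its quoted items run from never to always. Clusters built on these items may also differ in which symptoms they carry, and baseline adjustment overlaps with cluster membership. This stands as a caution. It argues for an ordinal model where needed, but gives no reason for only two categories.
- **Response is the question asked.** 3c and 3d speak of response, 3d needs the classification, and an exploratory cohort needs no regulatory reason for its choice of outcome. This justifies keeping the split, but not making it the only cluster test.
- **A graded analysis by treatment type would not have 0.885 power.** Correct, as step 4 shows. The cluster effect must therefore be the main term.

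**Conclusion.** The point holds in a limited form. For the response part of Hypothesis 3c, the protocol fixes a less sensitive method than the one it uses for 3a and 3b, and gives no reason.

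The loss matters in the full sample only for effects of about 0.2 to 0.25. It is small at 0.3 and disappears from 0.4. At 0.3 it remains material for a comparison within one sex or for a cluster holding a tenth of the cohort. All figures rest on the assumptions listed in the check, and responder rates below 30% would make the loss larger.

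Nothing here shows that the study is underpowered against a stated target, since 3c has none. Nor does it make the responder analysis invalid. It is an avoidable loss of efficiency and a cheap improvement.

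**What to change.** In section 3.4.10, Aim 3:
- Make the main test of the response part of 3c the cluster effect on the graded LUTS Tool score at follow-up. Use the mixed model already named for 3a and 3b, adjusted for baseline score and treatment type. Say which score is used, and use an ordinal model if it is not suitable as continuous.
- Treat cluster by treatment type as a secondary, exploratory term and state that its power is low.
- Keep the responsive/unresponsive classification for description per cluster or for a secondary logistic regression, and for Hypothesis 3d.

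The cost is a few sentences. No new data or visits are needed, and the model is already in the plan unless an ordinal one is required. The small downside is that the headline for 3c becomes a mean difference and not a responder rate, which is still reported.
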